2. PROTOCOL SYNOPSIS AND RESEARCH SUMMARY

2.1 Purpose

Given that many patients with HCC are not surgical candidates (for either resection or transplant), PLA techniques have become the standard non-operative approach. Non-randomized data have shown that the local control of HIGRT is comparable to that of PLA. Direct comparison of these two modalities via a randomized controlled clinical trial is the next logical step.

This research protocol will directly compare Percutaneous Local Ablation (PLA) to Hypofractionated Image-Guided Radiation Therapy (HIGRT) for patients with Hepatocellular Carcinoma (HCC) who are not surgical candidates or decline surgery while undergoing care at the Durham VA or at Duke Cancer Center.

Primary Objective

To compare change in Quality of Life (QOL), as defined by the European Organization for Research and Treatment of Cancer Quality of Life Questionnaire Core-30 (EORTC C-30), from baseline to 1 month post treatment in patients receiving PLA vs HIGRT.

Secondary Objectives

1. To estimate the difference in change in QOL in patients receiving PLA vs HIGRT, as measured EORTC C-30, from baseline to 3 months post-treatment
2. To estimate the difference in change in QOL in patients receiving PLA vs HIGRT, as measured EORTC C-30, from baseline to 6 months post-treatment
3. To estimate the difference in change in QOL in patients receiving PLA vs HIGRT, as measured by FACT-Hep, from baseline to 1 month, baseline to 3 months and baseline to 6 months post-treatment
4. To assess for grade ≥ 2 acute toxicity within 90 days of treatment initiation
5. To estimate the total healthcare system cost associated with PLA vs HIGRT from time of intervention through 90 days post treatment

Exploratory Objectives

1. To assess for grade 3+ late toxicity (>90 days post ablative therapy or radiation therapy)
2. To evaluate local control at the treated site within the liver
3. To evaluate distant liver recurrence (intrahepatic lesions other than treated lesion)
4. To evaluate median progression free survival (PFS)
5. To evaluate median overall survival (OS)

Hypotheses

For the primary endpoint of change in QOL at 1 month post treatment versus baseline, HIGRT will have significantly better patient reported global QOL than PLA.

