2.2.3 Data Analysis and Statistical Considerations

Ninety patients will be randomized with equal allocation to the two arms. Randomization will be stratified by whether the baseline global QOL score is < 60 or ≥ 60 , where QOL is measured by the EORTC QLQ-C30 scale (i.e., the European Organization for Research and Treatment of Cancer Quality of Life Questionnaire Core-30) which has a score range of 0-100. The primary outcome is the change in QOL from baseline to 1 month. We anticipate that approximately 10% of the accrued patients will be withdrawn before 1 month, leaving 80 evaluable patients to be used in the statistical analyses. The general linear model will be used to test for an arm effect (in patients receiving PLA vs HIGRT) by regressing the change in QOL on arm, controlling for the baseline value of QOL and the Child Pugh score. To calculate the power of the arm effect (in patients receiving PLA vs HIGRT) on change in QOL, we first note that the standard deviation of a normally distributed change score (SD_c) depends upon the SD of the pre-score, the SD of the post-score, and the Pearson correlation (ρ) between the two scores. If the SD's of the pre-score and the post-score are assumed equal and the correlation between them is 0.50, then $SD_c = SD$. For purposes of the power calculation, we assume that $SD=10$ and $\rho = 0.5$; therefore $SD_c = 10$. Assuming 40 evaluable patients per arm, the two-sample t-test (1-sided alpha = 0.10) of an arm difference in change across time in QOL has power 0.82 when the true arm difference in change score is 5 (i.e., 50% of SD_c). An arm difference of 50% of a standard deviation of an outcome variable is generally considered to be a "medium"-sized effect. In order to have 80 evaluable patients, 90 patients will be accrued (assuming ~10% drop out prior to the 1 month EOTRC QOL-C30 questionnaire).

After randomization, patients who have consented to study, but in the clinical judgement of the treating physician are no longer candidates for the randomized treatment, will continue to be evaluable for all study endpoints if treated with MWA or HIGRT (per PI approval). The primary analysis will be intent-to-treat (i.e., treatment arm as randomized). A sensitivity analysis will be conducted with patients categorized by treatment received.

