Ninety patients will be randomized with equal allocation to the two arms. Randomization will be stratified by whether the baseline global QOL score is < 60 or ≥ 60 , where QOL is measured by the EORTC QLQ-C30 scale. We anticipate that approximately 10% of the accrued patients will withdraw before 1 month, leaving 80 evaluable patients to be used in the statistical analyses. The general linear model will be used to test for an arm effect (in patients receiving PLA vs HIGRT) by regressing change across time in QOL on arm, controlling for the baseline value of QOL, Child Pugh score, and time between baseline and end of treatment. To calculate the power of the arm effect (in patients receiving PLA vs HIGRT) on change in QOL, we first note that the standard deviation of a normally distributed change score (SD_C) depends upon the SD of the pre-score, the SD of the post-score, and the Pearson correlation (ρ) between the two scores. If the SD's of the pre-score and the post-score are assumed equal and the correlation between them is 0.50, then $SD_C = SD$. For purposes of the power calculation we assume that $SD=10$ and $\rho = 0.5$; therefore $SD_C = 10$. Assuming 40 evaluable patients per arm, the two-sample t-test (1-sided alpha = 0.10) of an arm difference in change across time in QOL has power 0.82 when the true arm difference in change score is 5 (i.e., 50% of SD_C). An arm difference of 50% of a standard deviation of an outcome variable is generally considered to be a "medium"-sized effect. In order to have 40 evaluable patients per treatment arm, 90 patients will be accrued (assuming drop out prior to the 1 month EORTC QOL-C30 questionnaire).

After randomization, patients may decline the randomized treatment but will continue to be evaluable for all study outcomes if treated with MWA or HIGRT. All endpoints will be analyzed per randomized arm and per treatment delivered. If the patient does not receive either SBRT or MWA, the patient will be withdrawn from the study.

Secondary Endpoints:

[figure not shown]

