5. *To estimate the total healthcare system cost associated with PLA vs HIGRT from time of intervention through 90 days post treatment.* Costs will be estimated based on national averages for billable charges for all codes associated with PLA vs HIGRT throughout the course of treatment and the post-treatment follow up. This includes costs associated with any hospitalizations related to either procedure. Total costs per arm will be described with boxplots. Arm differences in the health care cost will be estimated using the statistical method best suited to the observed distribution of cost in these data (for example, a single distribution generalized linear model specifying, perhaps, a Gamma distribution).

Exploratory Endpoints:

1. *To assess for late toxicity (>90 days post PLA or HIGRT).* Late toxicity will be defined as any Grade 3+ toxicity occurring after the completion of the treatment regimen up to 6 months post-PLA or HIGRT. The proportion of patients experiencing any type of late toxicity will be estimated with an exact 95% confidence interval, by arm.
2. *To evaluate local control at the treated site within the liver.* Time to local failure will be defined as the length of time from enrollment to local failure at the site of treated disease within the liver (within the PTV). Intrahepatic sites distinct from treated lesions and distant failures will be ignored and deaths will be censored. The distribution of time to local failure will be estimated with the Kaplan-Meier method, by arm.
3. *To estimate distant liver recurrence (intrahepatic lesions other than treated lesion).* Time to distant liver recurrence will be defined as the length of time from date of enrollment to intrahepatic failure not within the site of treated disease; distant failures will be ignored and deaths will be censored. The distribution of time to distant failure will be estimated with the Kaplan-Meier method, by arm.
4. *To estimate median progression-free survival (PFS).* PFS will be defined as the length of time from enrollment to local or distant failure or death, whichever comes first. The distribution of PFS will be estimated with the Kaplan-Meier method, by arm.
5. *To estimate median overall survival (OS).* Overall survival (OS) will be defined as the length of time from enrollment to death due to any cause. The distribution of OS will be estimated with the Kaplan-Meier method, by arm.

5. STUDY SCHEMA (Pooled patients from Durham VAMC and Duke)

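### Exploratory endpoints 2 and 3: local failure is bounded by the PTV, which ablation patients do not have and which conflicts with the lesion-based next sentence; cumulative incidence would be a cheap addition to Kaplan-Meier

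*Combined protocol and SAP*

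**What the plan says.** Section 4, Exploratory Endpoint 2, measures time from enrollment to "local failure at the site of treated disease within the liver (within the PTV", the last words being a parenthesis. The sentence after it reads: "Intrahepatic sites distinct from treated lesions and distant failures will be ignored and deaths will be censored". Exploratory Endpoint 3 carries a lesion-based heading, but its definition is "intrahepatic failure not within the site of treated disease; distant failures will be ignored and deaths will be censored". Both are estimated by Kaplan-Meier, by arm, with no planned test. No competing-risk method appears anywhere in the documents.

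Section 2.1 states the matching objectives without mentioning the PTV: "To evaluate local control at the treated site within the liver" and "To evaluate distant liver recurrence (intrahepatic lesions other than treated lesion", the latter closing its parenthesis there.

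Patients who do not receive their randomized treatment stay in the analysis. Section 2.2.3 says that those no longer candidates for it "will continue to be evaluable for all study endpoints if treated with MWA or HIGRT", and Section 4 says that "patients may decline the randomized treatment but will continue to be evaluable for all study outcomes if treated with MWA or HIGRT". Section 4 adds: "All endpoints will be analyzed per randomized arm and per treatment delivered".

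**The concern.** There are two separate matters.

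**(a) The event definition.** The PTV is constructed only in Section 8.6, by expanding the ITV 5-10 mm radially and 7-10 mm superior/inferiorly. Section 9, on ablation, constructs no such volume. The boundary can therefore be applied only to HIGRT-treated patients, although the endpoint is reported for both arms and by treatment delivered. Even within HIGRT-treated patients, the PTV clause and the lesion clause disagree. Two people following the text could score the same recurrence differently.

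**(b) The estimator.** Death before failure is censored. Kaplan-Meier then describes the cause-specific failure process, which is legitimate. The plan does not say that 1-KM will be reported as a probability of failure. A reader who takes a failure rate off the curve will, however, get a figure above the share of patients who actually fail, by an amount that depends on mortality.

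What is at stake is the clarity and interpretation of two exploratory descriptive curves.

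**Working it through.** **(a) Side-by-side reading.** Take a new nodule inside the PTV margin but separate from the treated lesion.

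| Text | Boundary | How the nodule is scored |
|---|---|---|
| Endpoint 2, defining sentence | PTV | Local failure |
| Endpoint 2, next sentence | Treated lesion | Ignored |
| Endpoint 3, heading | Treated lesion | Distant liver recurrence |
| Endpoint 3, definition, if the treated site means the PTV | PTV | Not counted |
| Section 2.1, objective 3 | Treated lesion | Distant liver recurrence |

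Elsewhere in the liver the two rules agree. For a patient treated with microwave ablation, including one randomized to HIGRT, the PTV rows cannot be applied at all. The documents give no recurrence counts by location, so the number and direction of reclassified events cannot be computed.

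**(b) Size of the gap between 1-KM and cumulative incidence.** The plan gives no figure for these endpoints to reproduce, so this is an illustration.

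Inputs:
- Two-year local control of 80%, inside the 70-90% at 1-2 years that Section 3.1 reports for HIGRT. No rate is given for microwave ablation.
- One- and two-year survival from the Appendix Child-Pugh table: class A 100% and 85%; class B 81% and 57%.
- Assumed: independent hazards, constant within each year.

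Local failure hazard: l = -ln(0.80)/2 = 0.1116 per year.

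Death hazards d in years 1 and 2:
- A: 0, then -ln(0.85) = 0.1625.
- B: -ln(0.81) = 0.2107, then -ln(0.57/0.81) = 0.3514.

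Each year adds S × l/(l+d) × (1 - exp(-(l+d))) to the cumulative incidence, where S is the probability of being alive and free of local failure at the start of that year.

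- A: 10.56% + 8.73% = 19.29%.
- B: 9.54% + 6.47% = 16.01%.
- 1-KM at two years: 20.0%.
- Gaps: 0.71 points (A) and 3.99 points (B).
- Per 45 patients: 9.0 failures implied by 1-KM, against 8.7 (A) or 7.2 (B).

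A simulation of 2,000,000 patients gives the same 19.29% and 16.01%.

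Sensitivity to the control rate, at two years:

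| Two-year control | 1-KM | Cumulative incidence, A | Cumulative incidence, B |
|---|---|---|---|
| 90% | 10.0% | 9.6% | 8.0% |
| 80% | 20.0% | 19.3% | 16.0% |
| 70% | 30.0% | 29.0% | 24.2% |

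For scale, the binomial standard error at 20% with 45 patients is sqrt(0.2 × 0.8/45) = 6.0 points.

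Three years requires extrapolation. There 1-KM = 1 - exp(-3 × 0.1116) = 28.4%. With constant hazards, the cumulative incidence is l/(l+d) × (1 - exp(-3(l+d))):
- A, d = -ln(0.85)/2 = 0.0813: 25.4%. This hazard implies 92% alive at one year, against the Appendix's 100%.
- B, d = -ln(0.57)/2 = 0.2811: 19.7%.
- Section 10.5's expectation of about 20% alive beyond three years, d = ln(5)/3 = 0.5365: 14.8%.

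Carrying the Appendix's second-year hazard into year three instead gives 25.9% (A) and 20.1% (B). The 20%-alive case implies about 58% and 34% alive at one and two years, below even the class B figures, so it is only an outer bound.

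**The case against.** The phrase about the site of treated disease works for both treatments, and the PTV parenthesis can be read as a radiotherapy gloss on it. The conflict is confined to separate nodules inside the PTV, and Endpoint 3 does not itself use the term. Ablation is not without a target region either: Section 9.3 aims for a 0.5 cm margin, and Section 1 describes an intentional margin of 0.5-1 cm. On the estimator, censoring deaths is openly declared, suits an aim worded as local control, and moves the illustrated two-year figure by less than one standard error. A lesion-only rule also has a drawback, since radiotherapy deliberately treats a margin. The curves are exploratory and support no decision.

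Much of this is right about scale. The conflict is narrow, the estimator is a valid choice, and the consequence is limited. It does not remove the defect in the definition. The ablation margin is a procedural aim that the endpoint text never invokes. Reading the parenthesis as a gloss leaves the two sentences in disagreement for HIGRT patients, who do have a PTV. For ablation patients, the lesion sentence already leaves off-lesion recurrences out of local failure, so the lesion rule changes nothing for them.

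**Conclusion.** The point holds. Part (a) is a defect in the definition: one boundary exists for only one of the two treatments and contradicts the sentence that follows it. Its numerical effect is unknown.

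Part (b) is an improvement to a valid analysis. Under the stated assumptions, reading 1-KM as a probability overstates two-year local failure by 0.4 to 1.0 points with class A survival and by 2.0 to 5.8 points with class B survival, across 90% to 70% control. The gap is systematic but no larger than sampling error in an arm of 45. The class B figures may be pessimistic, because that class includes B9, which Section 6.2 excludes. No rate is given for distant liver recurrence, so no size is claimed for Endpoint 3. No between-arm distortion is claimed; that would need mortality to differ by arm.

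The change should be made, ideally before recurrences are classified, mainly on the strength of (a).

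**What to change.** **(a)** Delete the PTV parenthesis from Exploratory Endpoint 2 and apply the lesion-based rule already in the text to every patient, whichever treatment was delivered. Failure at the site of a treated lesion is local failure; any other intrahepatic lesion is distant liver recurrence, so that Endpoint 3 is the exact complement. State once, for both treatments, how a recurrence touching a treated lesion is scored, for example as local. The downside is that an off-lesion recurrence inside a PTV counts as distant liver recurrence. If the investigators prefer to include a margin, it should be one stated imaging distance from the treated lesion, identical for both treatments and used in both endpoints.

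**(b)** For both endpoints, treat death before the failure of interest as a competing event and estimate cumulative incidence by arm (Aalen-Johansen). Kaplan-Meier with deaths censored may stay as a labelled cause-specific summary, and stays for PFS and OS.

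**Cost.** Definition wording and slightly more analysis work. Deaths are already collected for OS. Section 10.5 does not say that recurrence location is recorded, but Endpoints 2 and 3 as written already need treated site versus other site, so the lesion rule asks for no further data item. Recurrences would no longer have to be matched to a radiotherapy plan. Where a report does not give the site, the images must be checked, as the current wording already requires.

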6.1 Inclusion Criteria

1. Patient has signed informed consent
2. HCC diagnosed either by histology/pathology or Liver Imaging Reporting and Data System (LIRADS 5 per the ACR's LIRADS criteria¹⁰) by CT or MRI
3. Patient is 18 years or older
4. ECOG Performance status of 0-2
5. Child Pugh score A5, A6, B7 or B8 (see Appendix)
6. Lesion \leq 5cm in size
7. \leq 3 lesions in the liver to be treated on protocol
8. Lesion amenable to treatment with both PLA and HIGRT; for PLA treatment this requires the lesion be visible via ultrasound and/or non-contrast CT or feasible per treating physician

6.2 Exclusion Criteria

1. Child Pugh score B9 or C10
2. Fluctuating ascites
3. Inability to complete baseline QOL forms
4. Concurrent administration of systemic therapy for HCC

5. Prior liver RT is an exclusion unless subject participation is approved by the PI
6. Positive serum pregnancy test

7. INVESTIGATIONAL PLAN

7.1 Study Design

- 90 patients will be accrued to this prospective, randomized multi-institutional study.
- Please refer to study schema in section 5.
- Eligible subject population is outlined in section 6.

7.1.1 Stratification

Patients will be stratified by whether their baseline value on the EORTC QLQ-C30 is <60 or ≥ 60. Two randomization strata will be formed according to the patient's baseline value on the European Organization for Research and Treatment of Cancer Quality of Life Questionnaire Core-30 (QLQ-C30) [i.e., <60 and ≥ 60].

7.1.2 Randomization

Patients will be sequentially randomized with equal allocation to the two arms in Research Electronic Data Capture (REDCap).

7.1.3 Safety Considerations

An **interim analysis** will be performed after the first 40 patients have been followed for 90 days after completion of study therapy. Accrual will not be halted during this analysis. All treatment-related grade 4-5 AEs occurring within 90 days of treatment will be tabulated and reviewed. If > 20% of patients experience grade 4-5 AEs attributable to treatment, a decision will be made to either: 1) halt the trial and all further accrual, 2) amend the protocol for more aggressive dose modification and/or 3) institute additional clinical monitoring.

Anticipated risks associated with PLA include:

- pain (muscle aches or spasm may occur for 3-5 days)
- nausea/vomiting
- infection
- fever
- liver damage
- blood vessel/nerve damage; this could require admission to hospital

Rare but very serious PLA risks include:

- liver damage which could cause liver failure
- bleeding from the liver which could be life threatening
- liver abscess (serious infection)

Anticipated risks associated with HIGRT include:

- fatigue
- pain
- nausea/vomiting

- **Rare but very serious HIGRT risks include:**
- liver damage which could cause liver failure
- rib fracture
- chest wall pain

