At Duke and the VAMC respective liver multi-disciplinary conferences meet 2-4 times a month and there are typically 3-4 patients presented at each tumor board who may be potentially eligible for this study. We anticipate accruing 20-30 patients annually.

As a secondary objective, the arm difference in the change in QOL from baseline to month 1 as measured by the Functional Assessment of Cancer Therapy-Hepatobiliary (FACT-Hep, version 4) will be calculated with its 95% confidence interval.

Please see section 5 below for more information regarding secondary and exploratory objectives.

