Board (DSMB). The primary focus of the SOC is review of safety data, toxicities and new information that may affect subject safety or efficacy. Annual safety reviews includes but may not be limited to review of safety data, enrollment status, stopping rules if applicable, accrual, toxicities, reference literature, and interim analyses as provided by the sponsor-investigator. The SOC in concert with the DCI Monitoring Team oversees the conduct of DUHS cancer-related, sponsor-investigator greater-than-minimal-risk intervention studies that do not have an external monitoring plan, ensuring subject safety and that the protocol is conducted, recorded and reported in accordance with the protocol, standing operating procedures (SOPs), Good Clinical Practice (GCP), and applicable regulatory requirements.

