18.2 Monitoring

The Duke Cancer Institute (DCI) Monitoring Team will conduct monitoring visits to ensure subject safety and to ensure that the protocol is conducted, recorded, and reported in accordance with the protocol, standard operating procedures, good clinical practice, and applicable regulatory requirements

This clinical research study will be monitored both internally by the PI and institutionally by the Duke Cancer Institute (DCI). In terms of internal review the PI will continuously monitor and tabulate adverse events. Appropriate reporting to the Duke University Medical Center IRB will be made. If an unexpected frequency of Grade III or IV events occur, depending on their nature, action appropriate to the nature and frequency of these adverse events will be taken. This may require a protocol amendment, dose de-escalation, or potentially closure of the study. The PI of this study will also continuously monitor the conduct, data, and safety of this study to ensure that:

Interim analyses occur as scheduled;

Stopping rules for toxicity and/or response are met;

Risk/benefit ratio is not altered to the detriment of the subjects;

Appropriate internal monitoring of AEs and outcomes is done;

Over-accrual does not occur;

Under-accrual is addressed with appropriate amendments or actions;

Data are being appropriately collected in a reasonably timely manner.

DCI review and monitoring of this protocol occurs in accordance with the NCI-approved Data and Safety Monitoring Plan. Briefly, protocol review begins with an initial review by the Cancer Protocol Committee (CPC), which assesses the ethics and safety of the protocol. Documentation of these assessments will be maintained. Formal, independent monitoring will be conducted by the DCI Monitoring Team after the first 3 subjects are enrolled, followed by annual monitoring of 1-3 subjects until the study is closed to enrollment and subjects are no longer receiving study interventions that are more than minimal risk. DCI Monitoring Team reports and

additional data/safety/toxicity reports submitted by the PI will be reviewed by the Safety Oversight Committee (SOC) on an annual basis.

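### The only numeric toxicity trigger is evaluated once, on the first 40 patients, so 50 of the 90 never enter it and no later look re-checks it

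*Combined protocol and SAP*

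**What the plan says.** Section 2.2.3: "Ninety patients will be randomized with equal allocation to the two arms", and "We anticipate accruing 20-30 patients annually".

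Section 7.1.3: the interim safety analysis "will be performed after the first 40 patients have been followed for 90 days after completion of study therapy. Accrual will not be halted" while it runs. The trigger is more than 20% of patients with grade 4-5 events attributable to treatment. If it is met, the choices are to stop the trial and accrual, or to "2) amend the protocol for more aggressive dose modification and/or 3) institute additional clinical monitoring". No other section gives a toxicity limit with a number, and none applies this one before or after the 40-patient look.

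Section 18.1: the annual committee review covers safety data and toxicities, and also "stopping rules if applicable, accrual, toxicities, reference literature, and interim analyses as provided by the sponsor-investigator".

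Section 18.2: the principal investigator tabulates adverse events continuously, and "If an unexpected frequency of Grade III or IV events occur, depending on their nature, action appropriate to the nature and frequency" of those events is to be taken. The same section allows extra monitoring when serious or unexpected toxicity is more frequent than expected, with no grade limit.

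The heading of section 18.1 states that 18.1 to 18.4 apply to the study team at Duke. Section 12 has no such limit: events are graded up to 5 (fatal), a fatal outcome is a serious adverse event, and serious adverse events go to the IRB.

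**The concern.** Section 7.1.3 names liver failure as a rare but very serious risk in both arms, and life-threatening bleeding from the liver with ablation. A numeric trigger commits the sponsor in advance to a decision at a stated level of harm. Here that commitment covers only the first 40 patients.

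Two consequences follow. A grade 4-5 rate above 20% that becomes visible only in later patients, or that narrowly misses the trigger at the look, meets no numeric limit afterwards. And if the look does trigger and the trial goes on with an amendment or added monitoring, the plan never re-applies the figure, so nothing pre-specified shows whether the change worked. The second gap needs no assumption about event rates.

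Two drafting gaps bear on what is left. The ongoing action clause and the interim rule count different grades, and only the interim rule names fatal events. As written, the arrangements in section 18 do not extend to patients treated at the Durham VA.

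**Working it through.** **The plan's own figure.** The documents give no operating characteristics for the toxicity rule, so there is nothing to reproduce.

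**Inputs.** 90 patients and 20-30 a year (2.2.3); one look at 40 patients with 90 days of follow-up, trigger above 20% (7.1.3); HIGRT over up to 3 weeks, about 0.7 month (8.6). Lag from enrolment to maturity: 3 to 3.7 months, ignoring any wait for treatment.

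**Timing.** Month of the look = 40/rate × 12 + lag.
- 30 a year: 16 + 3 = month 19 at the earliest.
- 20 a year: 24 + 3.7 = about month 28 at the latest.

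Enrolled by then = 40 + rate/12 × lag.
- Lowest: 40 + 20/12 × 3 = 45.
- Highest: 40 + 30/12 × 3.7 = about 49.

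An assumed wait of 0-2 months before treatment widens 45-49 to 45-54.

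**Coverage.** 40/90 = 44% are counted; 50/90 = 56% never are.

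**The single look.** More than 20% of 40 means at least 9 patients, taking both arms together. The binomial probability P(X ≥ 9; n = 40) is 0.015, 0.41 and 0.89 at true rates of 10%, 20% and 30%. Exactly 8 of 40 does not trigger.

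**Re-applying the same figure after patient 40.** Illustrative cumulative looks at 40, 60, 80 and 90 patients need at least 9, 13, 17 and 19 events. The exact calculation carries forward the distribution of event counts that have not yet triggered. The cumulative probability of having triggered is:

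| True rate | 40 | 60 | 80 | 90 |
|---|---|---|---|---|
| 10% | 0.015 | 0.018 | 0.018 | 0.018 |
| 20% | 0.407 | 0.508 | 0.570 | 0.598 |
| 30% | 0.889 | 0.957 | 0.982 | 0.988 |

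Shifting the later looks to where annual reviews might fall (for example 40, 53, 73 and 90) gives 0.023, 0.64 and 0.99. In round terms: about 2%, 0.60-0.64 and 0.99.

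**Looks before patient 40.** Evaluable patients at the first annual review = rate × (1 − lag/12). At 20 a year with a 3.7-month lag this is 20 × 0.69, or 13-14; at 30 a year with a 3-month lag it is 30 × 0.75, or about 22. With 13 or 14 patients, 3 events exceed 20%. At a true rate of 10%, that first look alone triggers with probability 0.13 (n = 13) or 0.16 (n = 14). The whole annual schedule then triggers with probability about 0.15-0.18. Across the accrual range the figure is about 5-18%, against 1.5% for the single look.

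**Grades and scope side by side.**

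| Provision | Grades named | Number | Patients covered |
|---|---|---|---|
| 7.1.3 interim rule | 4-5 | >20% | first 40 |
| 18.2 action clause | III-IV | none | Duke |
| 18.2 additional monitoring | no limit | none | Duke |
| 12.2.1 serious event reporting | no limit; fatal included | none | all |

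**The case against.** The strongest reply is that one formal look backed by continuous qualitative review is a legitimate design for two treatments already in use. The investigator tabulates all adverse events, the annual committee's main task is safety data and toxicities, and section 7.5 lets the investigator end the study at any time.

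That reply defeats a stronger reading that a reader might infer, namely that most patients have no working safety trigger and that deaths fall outside ongoing oversight. The documents do not support it. Fatal events are serious adverse events reported to the IRB, they fall within the investigator's tabulation, and the additional-monitoring clause in 18.2 has no grade limit. What is missing is a number, not safety review. The omission of grade V is confined to one sentence of 18.2. A formal threshold and a discretionary clause may also count different grades without contradicting each other, so the mismatch is a drafting gap.

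Two further objections stand in part. The 30% rate is only an illustration; the documents give no expected rate and call the serious risks rare. Repeated looks also have a price: at a true rate of exactly 20%, which does not exceed the plan's limit, triggering becomes clearly more likely. A reader might also infer that looks before patient 40 are nearly free. They are not, because a review of 13-14 patients can trigger on 3 events.

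None of this supplies a numeric check on the last 50 patients or after a change in conduct. Nor does it bring VA patients under section 18.

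**Conclusion.** The point holds as a gap in the numeric trigger, not in safety review as a whole. The coverage result (50 of 90 patients, 56%) and the missing re-check after an amendment or added monitoring come straight from the text. The timing rests on steady accrual at the planned rate and on treatment starting promptly.

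The probabilities assume a constant event rate, independent patients and one denominator for both arms; section 7.1.3 does not say whether the 20% is pooled or per arm. If it were read per arm with 20 patients each, the trigger would be 5 of 20, and the 0.89 at a true 30% would become 0.76 for that arm. The coverage finding would not change.

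This is an inexpensive improvement that should be made. It does not undermine the primary quality-of-life comparison.

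**What to change.** Keep the 40-patient look. State in 7.1.3 that the plan's own figure of more than 20% is re-evaluated on cumulative data pooled from both sites, at the safety reviews after patient 40 and after any change made under option 2 or 3, until the last patient reaches 90 days.

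Reconcile the grades counted in 7.1.3 and 18.2 so that fatal events are treated consistently. State how VA patients are covered, since 18.1-18.4 apply to Duke only. Say also who assembles the pooled safety data: section 13.3.2 sets up two parallel databases, and section 17 keeps VA data from Duke data-entry staff.

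The cost is protocol wording, an arrangement for pooled safety tables, and the extra triggers shown in the table. A trigger opens a choice among the three existing options; it does not stop the trial automatically. Whether to add looks before patient 40 is a trade-off for the sponsor.
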